## 1.0 PROTOCOL SUMMARY AND/OR SCHEMA

This is a safety study to evaluate toxicity and other clinical outcomes of whole lung intensity-modulated radiation therapy (IMRT) following standard treatment in patients with synovial sarcoma and lung metastases. Patients who received standard therapy for synovial sarcoma will be assessed for residual disease in the lungs by post-therapy imaging. Patients with pulmonary metastases  $\leq 2$  cm will then be eligible to receive Whole Lung Irradiation (WLI). The treatment plan will involve 1500 cGy of radiation delivered using IMRT in 150 cGy fractions.

Following completion of treatment, patients will have CT chest, physical exams, and toxicity assessments at 3, 6, 12, 18, and 24 months (+/-3 weeks for 3 and 6 months and +/-6 weeks for 12, 18, and 24 months), an echocardiogram at 6, 12, and 24 months, and pulmonary function tests at 6 and 24 months.

Fifteen patients will be enrolled in 6 years. The duration of the study will be 6 years.

## 2.1 OBJECTIVES AND SCIENTIFIC AIMS

Primary objective

- To assess the overall toxicity rate at 1 year after whole lung IMRT in this patient population

Secondary objectives

- To determine rates of pulmonary failure-free survival after completion of whole lung IMRT.
- To determine rates of overall survival (OS) after completion of whole lung IMRT.

### **3.0 BACKGROUND AND RATIONALE**

#### **3.1 The usage of whole lung irradiation in the management of pulmonary metastases**

Whole lung irradiation (WLI) is standard of care in the treatment of patients with pulmonary metastases from rhabdomyosarcoma (RMS), Ewing Sarcoma, and Wilms Tumor. The dose of WLI in modern Children's Oncology Group (COG) protocols is 15Gy for RMS and Ewing Sarcoma and 12 Gy for Wilms tumor. WLI reduces the rates of lung recurrences in patients with RMS. In the European Intergroup Cooperative Ewing's Sarcoma Study (EICESS), WLI was associated with a trend to improved overall survival (OS), reduced pulmonary relapses and improved event-free survival (EFS). Similarly, patients with Wilms tumor with lung metastases at diagnosis demonstrate reduced pulmonary relapse when treated with WLI as demonstrated in both the UK Children's Cancer Study Group (UKCCSG) and the National Wilms Tumor Study Group (NWTSG). The UKCCSG also demonstrated an association between EFS with the use of WLI. Taken together, these studies demonstrate that WLI is an accepted and efficacious treatment in the management of pulmonary metastases from RMS, Ewing Sarcoma, and Wilms Tumor.

#### **3.2 Rationale for using whole lung irradiation in synovial sarcoma**

Synovial sarcoma comprises approximately 8% of all soft tissue sarcomas (STS) and is the third most common extremity STS. Synovial sarcoma is frequently a disease of young adults with a mean age of 30-40 years. About 6-18% of patients have distant metastases at presentation and the lungs are the most common site of metastases. In one series of patients <21 years of age with synovial sarcoma, rates of metastases at diagnosis are about 6% with the vast majority of metastases (86%) located in the lungs. An adult series reported 18% of patients with metastatic disease at time of presentation with 78% of metastases located in the lungs. In a Surveillance, Epidemiology and End Result (SEER) database study of 1,268 adult and pediatric patients with synovial sarcoma, the rate of distant disease at presentation was 13%.

In contrast to RMS, Ewing Sarcoma, and Wilms tumor, the use of WLI in patients with synovial sarcoma and lung metastases is not standard of care. In the recently closed COG phase III ARST0332 trial for non-rhabdomyosarcoma soft tissue sarcoma, which included synovial sarcomas, the use of WLI or focal radiation to the lungs was not allowed. However, like RMS and Ewing sarcoma, synovial sarcoma is a radiosensitive histology. In the non-metastatic setting, the use of radiotherapy has been shown in large series to be associated with local control and EFS in patients with localized disease.

Data indicate that local control of pulmonary metastases is associated with improved survival. In a study from this institution that included 41 pediatric patients <22 years old with synovial sarcoma, patients who underwent pulmonary metastasectomy had a 2-year OS of 65% compared to 0% among patients who did not undergo pulmonary metastasectomy. In this series, 10 of 41 patients could not undergo pulmonary metastasectomy due to diffuse non-resectable disease. A larger series examining pulmonary metastasectomy in all patients at this institution with soft tissue sarcoma (STS) and pulmonary metastases showed a 3-year overall survival rate of 46% in those patients who underwent complete resection of pulmonary metastases compared to 17% in patients with no resection. Of note, of the 20

patients in this series with long term survival, 13 relapsed in the lungs requiring repeat resections leading the authors to conclude that “pulmonary metastases frequently represent diffuse involvement of the lung parenchyma. As such, it is difficult to eradicate all foci of metastatic disease with resection.” A series from Japan that included pediatric and adult patients with STS demonstrated a 2-year actuarial survival rate of 49.7% from time of first pulmonary resection with the use of aggressive pulmonary metastasectomy.

In addition to metastasectomy, local therapy to the lung in the form of radiation has been shown to provide excellent local control and improved OS. A series from the University of Rochester using stereotactic body radiotherapy (SBRT) for pulmonary metastases from STS showed an 82% rate of local control at three years and an improvement in OS from .6 years to 2.1 years with the use of SBRT. Synovial sarcoma comprised 15% of the patient population in this study. A German study investigated the use of WLI to 12Gy with a boost of 50-60 Gy to the single metastases in eight patients. Complete remissions were achieved in 6 of 8 patients.

### **3.3 Delivering whole lung irradiation utilizing IMRT**

#### **3.3.1 Cardiac complications associated with thoracic radiation**

Cardiac morbidity is well-recognized sequelae of radiation therapy. Irradiation of the heart can affect the coronary arteries, cardiac valves, pericardium, myocardium, and endocardium^18. The complications can ensue while the patient is receiving radiation though many of the effects of radiation on the heart are not seen until years after the completion of radiation. With regard to late toxicity, the rates of radiation-induced cardiac disease are between 10-30% with the onset of symptoms ranging from 5-10 years post-treatment.

In an analysis of the Childhood Cancer Survivor Study cohort which included 14,358 five year survivors of cancer diagnosed under the age of 21, a dose-response relationship was seen with regard to rates of congestive heart failure (CHF), myocardial infarction, pericardial disease, and valvular disease with a significant increase in these late complications when cardiac radiation exposure exceeded 15Gy. Another study of childhood cancer survivors showed that the risk of dying as a result of cardiac disease was significantly higher in patients who had received an average radiation dose greater than 5Gy to the heart (RR 12.5) and was further increased at doses exceeding 15 Gy (RR 25.1). There was a linear relationship between radiation dose and risk of cardiac mortality.

The NWTSG reported the rates of congestive heart failure in a cohort of patients treated on NWTS 1-4. The RR of CHF was increased in females, by cumulative doxorubicin dose, lung irradiation, and abdominal irradiation. The risk of CHF increased by a factor of 1.6 for every 10Gy of lung irradiation.

#### **3.3.2 The use of IMRT to reduce the cardiotoxicity of WLI**

A dosimetry study performed at Northwestern University, compared WLI plans for 22 patients using standard anteroposterior-posteroanterior (S-RT) technique and cardiac-sparing IMRT (CS-IMRT). Dosimetric parameters were calculated for the

whole heart, right atrium, left atrium, right ventricle, left ventricle, liver and thyroid gland. The volume of the heart receiving 6Gy, 8Gy, 10Gy and 11.4Gy was significantly lower in the CS-IMRT plans as compared to the S-RT plans. This was also true for the left ventricle, right ventricle and myocardium. The volume of left atrium and right atrium receiving 10Gy or above was significantly less in the IMRT plans. Similarly, the volume of coronary vessels receiving  $\geq 11.4$ Gy was lower in the IMRT plans.

There is a recently completed multi-institutional protocol (IRB# 11-100), including this institution, investigating the feasibility of cardiac-sparing whole lung IMRT in children and young adults (<30 years old) with a diagnosis of Wilms tumor, Ewing Sarcoma or RMS and lung metastases.

### **3.3.3 Pulmonary toxicity following WLI**

There is no data on pulmonary toxicity following WLI delivered with IMRT. However, there have been studies examining acute and late toxicity in patients who received WLI delivered with conventional fractionation. Lung irradiation at higher doses is correlated with adverse events including pneumonitis, pneumonia, chronic cough, dyspnea, chest wall deformity, interstitial lung disease, and supplemental oxygen requirement. This study included patients who received up to 64.8 Gy of radiation. The mean lung irradiation dose was significant associated with adverse pulmonary outcome. In studies that examine patients treated with low-dose whole lung irradiation exclusively, there are often mild reductions in pulmonary function abnormalities with low rates of clinically symptomatic moderate or severe pulmonary symptoms on follow-up. In one study that examined patients with osteogenic sarcoma treated with 16Gy WLI, restrictive pulmonary function abnormalities present at 6 and 12 months post-irradiation resolved by 2 years and no patients reported any significant pulmonary symptoms or decrease in exercise tolerance. A second study of patients with Ewing Sarcoma treated with WLI showed a rate of late lung toxicity of .6 (on a 0-3 scale with 0 indicating no toxicity) and no severe pulmonary function test abnormalities among patients treated with WLI and no thoracic surgery. An additional study showed reductions in FEV1 in 50% of patients, reductions in total lung capacity in 60% of patients, and reductions in diffusing capacity in 81% of patients, but all but one patient had none or mild self-reported respiratory symptoms in follow-up. In one study of patients treated with WLI for Wilms Tumor, a failure of chest wall growth was thought to contribute to late effects on pulmonary function though the mean age of patients was young (3 years and 9 months) and the radiation dose delivered was 20Gy. Taken together, these results indicate that while pulmonary function test abnormalities are often seen after whole lung irradiation, the incidence of clinically significant pulmonary toxicity is low, particularly at low-doses of 15Gy, which is the dose prescribed in this protocol.

## **4.1 OVERVIEW OF STUDY DESIGN/INTERVENTION**

### **4.2 Design**

This is a single institution study involving patients with synovial sarcoma who have completed all standard therapy (e.g. surgery +/- radiation to the primary site) +/- any adjuvant chemotherapy. The sequence and types of therapy offered prior to WLI will likely vary based on primary tumor site, tumor resectability, extent of metastatic disease, performance status, and comorbidity. Each patient's therapy will be determined by the disease management team irrespective of participation on this protocol.

Patients are eligible for this protocol if their pulmonary metastases are present at diagnosis or develop over the course of treatment. After completion of all planned therapy, patients will be assessed with a CT scan of their lungs and a PET scan if the CT scan shows residual lung metastases. Assuming there is no residual pulmonary disease or that any remaining pulmonary metastases are  $\leq 2$  cm, patients will proceed to WLI. If there is gross disease in the lung  $>2$  cm, patients will be evaluated for metastasectomy. If they undergo metastasectomy and subsequently have no residual pulmonary disease or have pulmonary metastases  $\leq 2$  cm, they are eligible to receive WLI on this protocol. Patients will also have an echocardiogram and pulmonary function tests (PFTs) prior to initiation of whole lung irradiation to assess baseline cardiac and pulmonary function. Patients will be simulated for external beam radiation with the use of a 4D CT to account for respiratory motion, as per standard practice. Patients will be treated with IMRT to 1500cGy in 150cGy fractions.

After completion of WLI, patients will be followed by members of the Radiation Oncology department for toxicity evaluations and will be evaluated by physical exams and chest CT scans at 3, 6, 12, 18, and 24 months (+/-3-6 weeks depending on timepoint). Patients will also have echocardiograms at 6 months (+/- 3 weeks) and 12, and 24 months (+/- 6 weeks). Patients will also undergo pulmonary function tests (PFTs) at 6 months (+/- 3 weeks) and 24 months (+/- 6 weeks). Any severe toxicity due to radiation will be carefully evaluated and further accrual will be terminated if the level of toxicity is greater than expected. The protocol may be terminated or modified as determined by the principal investigator. Please see section 11.0 regarding specific dose limiting toxicities and stopping rules for the protocol.

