### **10.2 Evaluations After Treatment**

Patients will have follow-up visits with physical examinations at 3 and 6 months (+/- 3 weeks) and at 12, 18, and 24 months (+/- 6 weeks) following the completion of radiation therapy. CT scans of the chest will be obtained at 3 and 6 months (+/- 3 weeks) and at 12, 18, and 24 months (+/- 6 weeks). Echocardiograms will be obtained at 6 months (+/- 3 weeks) and at 12, and 24 months (+/- 6 weeks). PFTs will be obtained at 6 months (+/- 3 weeks) and at 24 months (+/- 6 weeks). TSH levels will be obtained at 12 and 24 months (+/- 6 weeks).

In order to obtain data on overall survival, routine chart reviews will be conducted until 5 years following the completion of treatment.

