### **12.2 Assessment of Secondary Objectives**

### **12.2.1 Assessment of Pulmonary Failure-Free Survival**

A CT scan of the chest will be obtained at 3 and 6 months (+/- 3 weeks) and at 12, 18, and 24 months (+/- 6 weeks) post-treatment. This study will use a modified Response Evaluation Criteria in Solid Tumor (RECIST) for assessment of tumor response. The baseline scan will be the pre-irradiation CT scan.

All patients will be assessed as failure or failure free as defined below. Pulmonary failure-free survival will be defined as survival with no progressive disease in the lungs. CR, PR, and SD will be considered failure-free.

For patients with measurable ( $\geq 5\text{mm}$  but  $<10\text{mm}$ ) lung lesions at the time of study entry:

- a. The investigator will identify up to 5 measurable lung lesions to be followed for response. The sum of the longest diameter (LD) for all target lesions will be calculated and reported as the disease measurement.
- b. Complete response (CR) is defined as the disappearance of all target lesions.
- c. Partial response (PR) is defined as at least a 30% decrease in the disease measurement, taking as reference the pre-irradiation CT scan.
- d. Progressive disease (PD) is defined as at least a 20% increase in the disease measurement, taking as reference the smallest disease measurement recorded since start of treatment, or the appearance of one or more new lung lesions.
- e. Stable disease (SD) is neither sufficient shrinkage to qualify for PR nor sufficient increase to qualify for PD.

For patients with no measurable disease present at baseline:

- a. Stable disease (SD) is defined as no appearance of measurable lesions in the treated area
- b. Progressive disease (PD) is defined as the appearance of measurable lesions on post-treatment scans and will be considered failure-free if no measurable lesions develop.

**12.2.2 Assessment of overall survival** will be performed for each patient using clinical data and information from the social security database.

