### **14.0 BIOSTATISTICS**

The primary objective of this protocol is to assess the safety of whole lung IMRT following standard treatment in patients with synovial sarcoma and lung metastases. To this end we will enroll 15 eligible patients which will take about 6 years. Due to this long enrollment time the safety endpoint

will include both acute (<=3 months from the end of WLI) and late toxicities (>3 months from the end of WLI). Namely, we will evaluate the rate of any grade 3 toxicities (including pneumonitis, esophagitis, pericarditis and cardiac dysfunction) by using Kaplan-Meier estimation. If a patient withdraws from the protocol (expected to be 10% within 1 year), or dies without any grade 3 toxicities (expected to be 50% at 1 year) he/she will be regarded as a censoring at such time points. We will not use a competing risks analysis because it is expected that the withdrawal and death are independent from toxicities, and the actuarial estimate is believed to be more illustrative of the toxicity profile than the cumulative incidence rate by regarding death as a competing risk. For the decision rule we will look at the 1-year toxicity rate. If, the higher bound of the 85%, 1-sided confidence interval of the 1-year toxicity rate based on the (one minus) Kaplan-Meier estimate is lower than 0.25 than we will declare the whole lung IMRT procedure safe. This unusually high type 1 error rate, 15%, is used due to the rareness of such patients and the high progression/mortality rate without WLI. To roughly assess the power of the study with 15 patients, we simulated 10,000 datasets based on the above assumptions and examine the 1-year toxicity rate by Kaplan-Meier method. The following table shows probabilities of claiming whole lung IMRT safety under various values of the true 1-year toxicity rate.

True 1-year toxicity rate	0.05	0.10	0.15	0.20	0.25	0.30	0.35
Probability of claiming whole lung IMRT safe	0.894	0.712	0.536	0.364	0.243	0.154	0.094

As mentioned in Section 11.0, this study is also subject to early stopping if any radiation-related acute toxicities of grade 4 or higher are observed among the patients. If one of these events is observed in one patient, then the protocol will be closed to further accrual until reviewed by the principal investigator in conjunction with the investigators of the study.

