Rates of pulmonary failure-free survival will be assessed by cumulative incidence functions. To this end pulmonary failure is the event of interest and other progressions and death are considered as the competing risks. Overall survival rates will be estimated by the Kaplan-Meier method.

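### Deaths from lung progression that was never scanned are counted as competing deaths, so pulmonary failure incidence will be understated unless off-schedule scans capture them

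*Combined protocol and SAP*

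**What the plan says.** All references are to the combined protocol and SAP.

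- **What counts as failure.** Section 12.2.1, for patients with measurable lesions: "Progressive disease (PD) is defined as at least a 20% increase in the disease measurement", or new lung lesions. For patients without measurable disease: "Progressive disease (PD) is defined as the appearance of measurable lesions on post-treatment scans". It gives no clinical route to progression and no rule for a death from lung disease without a scan.
- **When scans happen.** Section 4.2 says that after treatment patients "will be evaluated by physical exams and chest CT scans at 3, 6, 12, 18, and 24 months". Section 10.2 adds the windows: "CT scans of the chest will be obtained at 3 and 6 months (+/- 3 weeks) and at 12, 18, and 24 months", with 6 weeks either side for the last three. The schedule in section 10.0 puts history and physical examination at the same visits. Off-schedule imaging is neither required nor barred.
- **How deaths are handled.** Section 14.0: "pulmonary failure is the event of interest and other progressions and death are considered as the competing risks". Deaths are not split by cause.
- **Who is analysed.** Section 13.0 restricts this endpoint to patients who finished the full radiation course and had one or more later chest CTs.
- **What the endpoint is.** Section 12.2.1: "Pulmonary failure-free survival will be defined as survival with no progressive disease in the lungs". Read literally, any death ends failure-free status, which does not match section 14.0.
- **Expected mortality.** Section 14.0 assumes that a patient "dies without any grade 3 toxicities (expected to be 50% at 1 year").

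**The concern.** Take a patient whose month-6 CT is clear, whose lung disease progresses at month 7 and who dies of it at month 10 with no further scan. Under sections 12.2.1 and 14.0 this is a competing death, not a pulmonary failure, and nothing elsewhere in the plan changes that.

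This could affect more than an odd case. Every patient has or has had lung metastases, and half are expected to die within a year. The patients with the fastest lung progression are the most likely to die before the next CT, so they are the ones moved out of the event of interest. Within the evaluable set, that misclassification can only lower the recorded incidence. Lung control is the trial's only efficacy measure besides overall survival, and it would look better than it was, by an amount that depends on how often patients happened to be scanned off schedule.

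**Working it through.** **The plan's own figures.** The documents state no expected rate or precision for pulmonary failure, so there is none to reproduce. The only operating characteristics are the toxicity table in section 14.0. Exponential times with 50% death and 10% withdrawal at 1 year reproduce its seven entries to within 2 points (for example 0.882 against 0.894, and 0.247 against 0.243). The same exponential 50% mortality is used below; withdrawal is ignored.

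**Scan gaps.** Nominally 6 months after month 6. With the windows, the gap from the month-6 to the month-12 scan can reach 6 months + 3 + 6 weeks, about 8.1 months. Later gaps can reach 6 months + 6 + 6 weeks, about 8.8 months. The calculation uses nominal times.

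**Assumptions not in the documents.** Constant hazard λ of lung progression. Constant hazard μ = ln 2 / m of death after progression, with median m of 3, 6 or 9 months. Lung disease accounts for 100% or 70% of year-1 deaths.

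**Formulas when all deaths are lung-related.** The probability of progressing and dying within t months is

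F(t) = 1 − [μ·exp(−λt) − λ·exp(−μt)] / (μ − λ), with λ solved from F(12) = 0.5.

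Progressions missed after the first CT, with scans at 3, 6 and 12 months: M = exp(−3λ)·F(3) + exp(−6λ)·F(6).

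Share with at least one CT: 1 − F(3). Shortfall in the evaluable set: M / (1 − F(3)).

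If a fraction q of missed cases have an off-schedule scan: (1 − q)·M / (1 − (1 − q)·F(3)).

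**Worked case, m = 3 months.** μ = 0.231 and λ = 0.095 per month.

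- F(3) = 0.072 and F(6) = 0.214.
- M = 0.752 × 0.072 + 0.566 × 0.214 = 0.054 + 0.121 = 0.175.
- Shortfall = 0.175 / 0.928 = 0.189.
- With q = 0.5: 0.088 / 0.964 = 0.091. With q = 0.8: 0.035 / 0.986 = 0.036.

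**All cases**, by simulation of 400,000 patients. In the 70% rows an independent non-lung death hazard is added, solved so that 50% still die by month 12. Incidences are 12-month percentages in the evaluable set; shortfalls are in points, from unrounded values.

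| Lung-related deaths | m (months) | True | Recorded, scheduled CT only | Shortfall, q = 0 | q = 0.5 | q = 0.8 |
|---|---|---|---|---|---|---|
| 100% | 3 | 65.4 | 46.6 | 18.8 | 9.0 | 3.5 |
| 100% | 6 | 86.6 | 74.4 | 12.2 | 5.9 | 2.3 |
| 100% | 9 | 98.7 | 92.8 | 5.9 | 2.8 | 1.1 |
| 70% | 3 | 49.8 | 34.4 | 15.5 | 7.5 | 3.0 |
| 70% | 6 | 69.2 | 57.3 | 11.9 | 5.7 | 2.2 |
| 70% | 9 | 85.2 | 75.8 | 9.4 | 4.6 | 1.8 |

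With q = 1 the shortfall is zero in every row.

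**In patients.** With scheduled CTs only, the misclassified share of all treated patients runs from 0.054 to 0.175. That is 15 × 0.054 = 0.8 to 15 × 0.175 = 2.6 patients.

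**Patients lost before any CT.** In these scenarios 7–10% die before month 3 and drop out under section 13.0. They are not competing deaths.

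**The case against.** The strongest reply has four parts.

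1. **Every driver of the size is assumed.** This stands. The documents give no lung progression rate, survival after progression, cause-of-death split or off-schedule scan rate, and some rows above imply that most patients progress in the lung within a year. The statement in section 3.2 that "the vast majority of metastases (86%) located in the lungs" describes where metastases were at diagnosis in patients under 21, not what patients die of. It cannot supply the missing split.
2. **Off-schedule scans may solve the problem.** This stands in part. Section 12.2.1 does not confine new lesions to scheduled scans. But the plan neither calls for such scans nor says that they count, so the estimate rests on unplanned practice.
3. **The deeper defect is the clash between sections 12.2.1 and 14.0.** If the former governed, any death would end failure-free status and this misclassification would largely cease to matter. That is a reason to settle the conflict. It does not cure the cumulative incidence analysis, which is the one section 14.0 specifies.
4. **Counting clinically attributed lung deaths as failures brings its own bias.** This stands. Section 11.0 lists pneumonitis and pulmonary fibrosis as treatment risks, and toxicity could be labelled as tumour failure. It argues for a sensitivity analysis, not a new main definition.

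Precision is also poor. A 95% interval around 50% with 15 patients is about ±1.96 × √(0.25/15) = ±25 points, wider than the shortfall. But the shortfall is systematic and cheap to expose.

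**Conclusion.** The point holds for patients with at least one follow-up CT: the rules as written record an unscanned lung death as a competing death. The 12-month shortfall is about 6–19 points with scheduled CTs only, 3–9 if half the missed cases are scanned off schedule, 1–4 if 80% are, and zero if all are. These figures rest on the assumptions listed, chiefly 50% mortality at 1 year, 70–100% of deaths lung-related and a 3–9 month median after progression.

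A reader might infer more than the documents support:

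- **That the rate is certainly understated.** It is not if off-schedule imaging captures every such progression, and nothing bars that imaging.
- **That every unscanned lung death becomes a competing death.** Counting all treated patients in the 100% rows gives a shortfall of 14–25 points (for example 68% true against 43% recorded at m = 3). Part of that comes from deaths before the first CT, which section 13.0 removes. They are a separate loss.
- **That the reported figure must fall below the truth for all treated patients.** The section 13.0 exclusion also removes early non-lung deaths, which pushes the other way. With 70% lung-related deaths and q = 0.8, the evaluable-set figure is 68.3% against 67.9% true in all treated patients at m = 6, and 84.1% against 82.8% at m = 9.
- **That the safety conclusion is affected.** This endpoint is secondary and has no decision rule; the primary toxicity rule does not use it.

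**What to change.** 1. In section 12.2.1, state that any chest imaging, scheduled or not, can establish lung progression, dated at that scan.
2. In section 14.0, keep the imaging-based cumulative incidence as the main analysis. Add a sensitivity analysis that counts as pulmonary failure those deaths after the last CT that are attributed to lung tumour progression or have unknown lung status, and that also includes treated patients with no follow-up CT. Report the two figures as a range.
3. Reconcile the endpoint definition in section 12.2.1, under which any death ends failure-free status, with section 14.0, under which death is a competing risk.

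The cost is a few sentences and no extra scans. Cause of death would have to be abstracted from the clinical records and chart review already used for overall survival (sections 10.2 and 12.2.2). That takes some judgement to separate tumour progression from radiation lung toxicity, and the upper figure will look less favourable.

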#### **Evaluation of SAE:**

Review of the patient record including the treatment dosimetry will be undertaken by the principal investigator and investigators of the study. The principal investigator in conjunction with the investigators of the study may decide to continue the protocol without modification, discontinue the study altogether, or to modify the protocol prior to enrolling more patients pending the results of the review.

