#### **Unacceptable Toxicity:**

Enrollment on the protocol will be suspended for WLI related acute toxicities  $\geq$  grade 4 radiation pneumonitis, esophagitis, pericarditis, cardiac dysfunction, and acute chest wall pain. If one of these events is observed in one patient, then the protocol will be closed to further accrual until review by the principal investigator in conjunction with the investigators of the study.

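### Section 4.2 promises to end accrual if toxicity exceeds expectation, but no count or rate criterion covers the primary endpoint, so nothing requires a pause once the safety verdict is lost

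*Combined protocol and SAP*

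**What the plan says.** Section 4.2 (Design) commits that "further accrual will be terminated if the level of toxicity is greater than expected". It adds "The protocol may be terminated or modified as determined by the principal investigator" and then "Please see section 11.0 regarding specific dose limiting toxicities and stopping rules for the protocol".

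Section 11.0 contains two relevant provisions:

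- Under Unacceptable Toxicity, enrolment is suspended for acute WLI-related events at or above "grade 4 radiation pneumonitis, esophagitis, pericarditis, cardiac dysfunction, and acute chest wall pain". The action is: "If one of these events is observed in one patient, then the protocol will be closed to further accrual until review". Section 14.0 repeats this as the early-stopping provision, without limiting it to the named toxicities.
- Under Evaluation of SAE, the record and dosimetry are reviewed, after which the investigators "may decide to continue the protocol without modification, discontinue the study altogether, or to modify the protocol". The last item of the SAE definition covers events of grade 3 or higher that are possibly related to WLI. That item ends by calling them adverse events, where serious adverse events is evidently meant.

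The safety verdict is defined in Section 14.0. The endpoint is any grade 3 toxicity, acute and late, estimated by Kaplan-Meier. The procedure is declared safe if "the higher bound of the 85%, 1-sided confidence interval of the 1-year toxicity rate" lies below 0.25. On sample size, "we will enroll 15 eligible patients which will take about 6 years".

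**The concern.** A reader who follows the cross-reference from Section 4.2 does not find what is promised. There is no expected level, and no count or rate of primary-endpoint events that would end or pause accrual. The one hard trigger concerns a different set of events. Grade 3 toxicities do not trip it, and neither do late toxicities of any grade, yet both count towards the verdict.

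The decision rule already fixes a point at which the verdict is lost. Accrual is slow, so that point can come while patients are still to be enrolled. Nothing in the plan then requires anyone to stop and decide whether further patients should be treated in a study whose safety claim cannot succeed.

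**Working it through.** **Inputs from Section 14.0.** 15 patients over about 6 years; 85% one-sided bound (z = 1.0364); threshold 0.25; censoring by withdrawal (10% at 1 year) and by death without grade 3 toxicity (50% at 1 year). **Not given in the documents:** the type of confidence interval, the accrual pattern and the timing of toxicity. These are assumptions below.

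**1. Reproduce the plan's table.** 10,000 simulated datasets per rate, exponential toxicity, withdrawal and death times, Greenwood variance, and a bound of 0 when there are no events.

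| True rate | 0.05 | 0.10 | 0.15 | 0.20 | 0.25 | 0.30 | 0.35 |
|---|---|---|---|---|---|---|---|
| Plan | 0.894 | 0.712 | 0.536 | 0.364 | 0.243 | 0.154 | 0.094 |
| Plain Greenwood | 0.884 | 0.704 | 0.524 | 0.356 | 0.241 | 0.154 | 0.088 |
| Log Greenwood | 0.887 | 0.710 | 0.530 | 0.365 | 0.249 | 0.159 | 0.092 |

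Both agree with the plan to within 0.02. A log-log bound does not (0.779 at a rate of 0.05). The plan therefore appears to have used a plain or log bound.

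**2. Smallest possible bound for k events.** The best case is k events before any censoring. Then p = k/15 and the plain bound is p + 1.0364 × √(p(1 − p)/15).

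- k = 1: 0.0667 + 1.0364 × 0.0644 = 0.133
- k = 2: 0.1333 + 1.0364 × 0.0878 = 0.224
- k = 3: 0.2000 + 1.0364 × 0.1033 = 0.307

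The log bound is 1 − S × exp(−1.0364 × √g), where g is the Greenwood sum. For k = 3, S = 0.8 and g = 1/(15×14) + 1/(14×13) + 1/(13×12) = 0.01667, so the bound is 1 − 0.8 × exp(−0.1338) = 0.300. For k = 1 and k = 2 it is 0.131 and 0.220.

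Enumerating every possible set of numbers at risk at three events confirms 0.307 and 0.300 as the minima; censoring before an event only raises the bound. In simulation no trial with three or more events was declared safe. If a few extra patients were treated, the result stands: with 18 patients and 3 events the plain bound is 0.1667 + 1.0364 × 0.0878 = 0.258, and the log bound is 0.253.

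With 2 events among 15, a log-log bound is at least 0.258 and an exact binomial bound is 0.287. Under either of those methods the second event already settles the verdict.

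**3. How often the third event comes before the last enrolment.** Uniform entry over 6 years, the plan's censoring, and nobody using discretion:

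| True rate | 0.10 | 0.15 | 0.20 | 0.25 | 0.35 |
|---|---|---|---|---|---|
| Constant hazard | 5% | 15% | 27% | 40% | 66% |
| All toxicity within 3 months | 12% | 29% | 47% | 63% | 86% |

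These are simulation results, good to about a percentage point. In the trials concerned, the mean number enrolled afterwards at a true rate of 0.25 is about 4.7 (constant hazard) or 5.6 (early toxicity). Averaged over all trials at that rate it is about 1.9 or 3.5. With 4-year accrual and constant hazard, the 0.25 and 0.35 figures become 37% and 62%.

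**4. Effect on the verdict.** Every trial that reaches a third event within 12 months already fails the rule. Pausing there changes no entry in the Section 14.0 table.

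**The case against.** The strongest reply is that oversight is not absent. WLI-related grade 3 events, early or late, evidently fall under SAE review, which can end the study. Section 17.2 requires SAEs to reach the IRB/PB within 5 calendar days, Section 16.2 describes an institutional monitoring committee, and the principal investigator may terminate at any time. A reader might infer that nothing monitors grade 3 toxicity, or that patients would necessarily go on being enrolled. The documents support neither reading. What is missing is narrower: a cumulative criterion. The frequencies above assume that discretion is never used and ignore the grade 4 suspension, so they are upper figures.

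Second, losing the verdict is not the same as excess toxicity. Three of 15 is 20%, below the 0.25 limit. By the plan's own table, safety is not declared in 1 − 0.712 = 29% of trials at a true rate of 0.10 and in 1 − 0.536 = 46% at 0.15. A reader might take the third event as proof of toxicity greater than expected; it is not. This stands, and it is why the remedy should be a pause for review and not a mandatory termination.

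Third, the primary objective in Section 2.1 is to estimate the 1-year toxicity rate, and such patients are rare. Closing accrual costs precision there as well as in the secondary endpoints. That also stands, but under a pause the investigators can weigh it and resume.

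Fourth, the count of three depends on an interval that the plan does not name. This too stands, and the interval has to be named first.

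**Conclusion.** The point holds in this form: Section 4.2 makes a commitment that Sections 11.0 and 14.0 do not carry out for the primary endpoint. Under a plain or log Greenwood bound with 15 patients, the third patient with an event within 12 months makes a declaration of safety impossible; under log-log or exact bounds the second does. That part is arithmetic and needs no accrual assumption.

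How many patients this affects is less certain. It rests on assumed uniform accrual, assumed toxicity timing and no use of discretion. On those terms the third event precedes the last enrolment in 5% to 12% of trials at a true rate of 0.10, rising to 66% to 86% at 0.35. The finding concerns futility of the safety claim. It does not show that whole lung IMRT is too toxic, nor that the existing review would fail to act.

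**What to change.** Reconcile Sections 4.2, 11.0 and 14.0:

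- Name the confidence-interval method in Section 14.0.
- State in all three sections that accrual pauses, for the investigator review already described in Section 11.0, when the number of patients with a primary-endpoint event within 12 months of WLI makes the 0.25 criterion unattainable. With 15 patients that is three under plain or log Greenwood; recompute it if another method or sample size is adopted. The investigators then decide whether accrual resumes.
- Say plainly that this is a futility pause on the safety claim. Either define the expected level that Section 4.2 mentions or replace that phrase with a reference to the pause.
- Specify which events count: grade 3 only or grade 3 and above, and whether attribution to WLI is required.
- Correct the last item of the SAE definition so that its status is clear.

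The cost is protocol wording and a running count. At true rates below the limit the pause would sometimes occur before the last enrolment: 15% to 29% of trials at 0.15 and 27% to 47% at 0.20 under the assumptions above. If accrual does not resume, fewer patients contribute to the 1-year toxicity estimate and to the secondary endpoints. The probability of declaring safety is unchanged at every true rate.
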